Inclusion criteria for participating children:

1. Age 10 to 14 years;
2. Live in the same household as primary caregiver who is part of PfR study;
3. Parent/caregiver gives consent to participate in the study;
4. Provision of consent to participate in the full study.

Inclusion criteria for facilitators:

1. Age 18 or older;
2. Facilitator who is involved in the delivery of the Parenting for Respectability programme;
3. Provision of consent to participate in the full study.

We will also conduct interviews with community development service officials and local leaders involved in the delivery of PfR. They will have the following inclusion criteria:

1. Age 18 or older;
2. Involvement in delivery of PfR, or existing leadership role in communities where PfR is delivered;
3. Provision of consent to participate in the full study.

11. Recruitment

This study will rely on SOS Uganda and local municipal staff to identify target clusters (i.e., villages or sub-villages) for recruitment in the study. We will first obtain community-level consent from community leaders to conduct the study. Potential parents will then be recruited from each cluster. We aim to recruit men as much as women, and will include equal numbers to receive the intervention, regardless of age.

By deliberately recruiting fathers, the project addresses the recurrent concern about lack of male involvement. The structure of the programme begins with single sex sessions, followed by mixed sex sessions, allowing men and women discuss sensitive issues initially without worrying of the perspectives of the other gender. We will randomly select one child between the ages of 10 and 14 per household to participate in the study, though not the intervention which is only delivered to adults.

Informed consent procedures will be administered by trained and supervised research personnel both verbally and in writing to account for low-literacy rates. They will be thoroughly trained and supervised by the co-principal investigators and co-investigators on recruitment, informed consent, and assessment procedures.

12. Randomisation

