Child maltreatment will be measured using an adapted version of the ISPCAN Child Abuse Screening Tool-Trial scale (13 items, ICAST-Trial) [26]. The original version of the ICAST-Trial was reduced from 27 items for adolescents to increase study feasibility due to the scale of the study. Child respondents will report on the overall frequency of maltreatment for male caregivers during the past month as well as for subscales on physical abuse (5 items; e.g., “In the past month, how often did your male parent figure hit, beat, or spank you with a hand?”) and emotional abuse (8 items; e.g., “In the past month, how often did your male parent figure in your household insult you, say mean things to you or swear at you?”). Each item ranges from 0 to more than 8 times and is summed to assess frequency of overall abuse as well as for each individual subscale.

[Time Frame: Baseline, 8-months post-baseline, and 12-months post-baseline]

Child maltreatment - physical and emotional abuse: ISPCAN Child Abuse Screening Tool-Trial Parent (ICAST-TC) - Child Report on Female Parent Figure

Child maltreatment will be measured using an adapted version of the ISPCAN Child Abuse Screening Tool-Trial scale (13 items, ICAST-Trial) [26]. The original version of the ICAST-Trial was reduced from 27 items for adolescents to increase study feasibility due to the scale of the study. Child respondents will report on the overall frequency of maltreatment for female caregivers during the past month as well as for subscales on physical abuse (5 items; e.g., “In the past month, how often did your female parent figure hit, beat, or spank you with a hand?”) and emotional abuse (8 items; e.g., “In the past month, how often did your female parent figure in your household insult you, say mean things to you or swear at you?”). Each item ranges from 0 to more than 8 times and is summed to assess frequency of overall abuse as well as for each individual subscale.

[Time Frame: Baseline, 8-months post-baseline, and 12-months post-baseline]

Intimate partner violence - perpetration: Revised Conflict Tactics Short Form - Parent Report

Perpetration of intimate partner violence (parent-report) will be measured using adapted versions of the Revised Conflict Tactics Scale Short Form (6 items; CTS2S) [27]. We will perpetration of emotional and physical violence against an intimate partner (e.g., “How often did you insult or shout or yell or swear at

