In addition, we are aware that research with vulnerable families can result in increased stress due to the disclosing of difficult personal information and the demands of meeting deliverables. We will also conduct weekly debriefing meetings with research personnel to discuss any potentially distressing events that may have occurred during data collection. Staff will also participate in one-on-one reviews at the end of each data collection wave to assess their performance and psychological needs.

23. Potential of harm

The focus of this study is to strengthen and evaluate the impact of a community-based parenting programme. We believe that the overall potential benefits of the research and intervention in reducing the risk of child maltreatment and partner conflict will outweigh potential risks of harm against participants. Nevertheless, we must consider two levels of potential harm: participation in the study and participation in the intervention.

Potential harm from the study

It is important to consider potential harm from participation in the study, no matter how small. There is a possibility that the opportunity to discuss parenting and parent-child relationships during interviews may prompt distress in the respondents [64]. All research personnel will be trained in ethical procedures and protocols concerning research with human subjects. During the consent stage, we will inform all participants that everything said will be confidential unless it becomes clear that they are at risk of significant harm or of putting anyone else at risk of harm. We will also inform participants that they do not have to answer any questions that they feel uncomfortable with and that they can stop the interview at any time without any negative consequences. In the case of participants not completing the baseline assessment, they will be excluded from the study.

Disclosure of harm

There is the possibility that participants may disclose harsh parenting practices that would reflect potential abuse or neglect of children. This study recognises that researchers have a responsibility towards children who may be at risk of abuse or neglect or any other risk of severe harm. It is to be noted that it is an ethical principle to provide help for children whom the research identifies as in need.

As a result, the following protocol is proposed to mitigate any potential harm to children or adults that might occur during the study:

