1. If information is disclosed that suggests that any member of the household is at risk of significant harm, the researcher will discuss concerns with the respondent at the end of the interview;
2. If the household member at risk of harm is a child, the researcher will discuss with the parent the possibilities for referral to child welfare, health organisations, and other services;
3. If the harm is considered to be significant, the research staff will inform local child protection services;

4. If severe abuse is disclosed in data collection, children will be immediately referred to social or medical services and the participant will be automatically excluded from the study;
5. If the decision is made to take action, the participant(s) will be informed and referral will be made;
6. All staff will also receive additional training from the research team on how to respond to these situations in alignment with the study's referral protocols;
7. Weekly supervision meetings with all field interviewers will allow discussion of issues that arise concerning harm to research subjects and children;
8. Finally, if we determine that respondents or their families have experienced significant harm as a result of participation in the research study (i.e., severe abuse, suicidality, intimate partner violence, or other potential psychological or physical injuries), we will cease further activities until these issues can be addressed adequately.

Consistent with the abovementioned protocols, the informed consent form will indicate that relevant information may have to be disclosed without respondents' consent if the participant or a household member poses a serious danger to the self or to others, or if there is evidence to suggest child abuse or neglect.

Mitigating potential harm from the intervention

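### Disclosure item 2 sends the researcher to the parent whenever a child is at risk, with no exception when the child's own interview implicates a parent figure

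*Protocol*

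**What the plan says.** Protocol section 23, under Disclosure of harm, gives an eight-item procedure. Its lead-in foresees that "participants may disclose harsh parenting practices that would reflect potential abuse or neglect of children". The items that matter here are:

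- Item 1: when someone in the household appears to be at risk of significant harm, the researcher raises the concern with the respondent once the interview is over.
- Item 2: "If the household member at risk of harm is a child, the researcher will discuss with the parent the possibilities for referral".
- Item 3: "If the harm is considered to be significant, the research staff will inform local child protection services".
- Item 4: on disclosure of severe abuse, "children will be immediately referred to social or medical services".
- Item 5: "If the decision is made to take action, the participant(s) will be informed and referral will be made".
- Item 6: "All staff will also receive additional training from the research team on how to respond to these situations", in line with referral protocols that this document does not reproduce.
- Item 7: weekly supervision meetings for interviewers.

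Section 10 makes it an inclusion criterion that the child should "Live in the same household as primary caregiver who is part of PfR study". Section 15 has children report on acts by each parent figure, for example "how often did your male parent figure hit, beat, or spank you with a hand".

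**The concern.** Item 2 names one person to speak to when a child is at risk, and that person is the parent. In this trial the child is also a respondent and is asked directly about the conduct of parent figures. The adult whom item 2 points to may therefore be the adult the child has just implicated, or that adult's partner.

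A parent who is approached soon after a child's interview can infer that the child said something, even if no answer is repeated. The child goes on living in that household. The study's own contact could then bring about the kind of harm that section 23 is written to mitigate.

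**Working it through.** No calculation decides this. The check sets the provisions side by side.

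**1. Is item 2 conditional?** No. It applies when the household member at risk is a child. It does not depend on who made the disclosure or who is implicated.

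**2. Is it limited to adult interviews?** Not by its wording. Item 1 speaks of the respondent, whereas item 2 speaks of the parent. The lead-in refers to participants, and section 10 sets inclusion criteria for children as participants. Item 4 covers severe abuse disclosed in data collection, which includes child interviews.

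**3. Is a child's report that implicates a parent figure foreseeable?** Yes. Section 15 gives the child 13 maltreatment items on the male parent figure, 13 on the female parent figure and 4 neglect items: 13 + 13 + 4 = 30 items on acts by a parent figure. There are a further 10 sexual-abuse items, whose sample question leaves the perpetrator open. All are asked at baseline, 8 months and 12 months, in a planned sample of approximately 1,080 children (section 8). Under section 18, data collectors read out the questions and help key in responses, so they may learn the answers during the interview. These counts show only that the situation can arise. They do not measure how often it would.

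**4. Does any other provision suspend item 2 or have to come before it?**

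| Provision | What it does | Suspends or precedes item 2? |
|---|---|---|
| Item 1 | Concern raised with the respondent (the child, in a child interview) | Does not replace item 2 |
| Item 3 | Child protection informed if harm is judged significant; no parental agreement needed | No order fixed |
| Item 4 | Immediate referral for severe abuse | Silent on contact with the parent |
| Item 6 | Training aligned with referral protocols | Content not shown |
| Item 7 | Weekly supervision | Item 2 does not wait for it |
| Item 8 | Activities stop once significant harm from taking part is established | Acts only afterwards |
| Consent statement after item 8 | Allows disclosure without the respondent's consent | Does not restrict disclosure to an implicated adult |
| Self-referral information (end of section 23) | Lists services for participants | Does not govern what researchers do |

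**5. Does item 5 add to this?** Only weakly. The participants to be informed are not defined and could be the child, the parent or both.

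Within this document, then, nothing removes or delays the contact that item 2 directs.

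**The case against.** The best case for the current text has four parts.

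- **Item 2 may be meant for adult interviews.** The lead-in most naturally describes adults talking about their own discipline, so the parent in item 2 may simply be the respondent. That reading is available, but the text does not confine item 2 to it.
- **Item 2 may be narrow.** It appears to refer back to item 1's risk of significant harm, so it would mostly operate where item 3 also brings in child protection. It also concerns options for referral and does not tell the researcher to pass on the child's answers. Both observations stand, and they limit the gap. They do not settle the order of contact, and a parent can draw an inference from being approached at all.
- **The detail may sit elsewhere.** The referral protocols behind item 6 may hold exactly this exception, and section 22 requires approval from two ethics bodies before the study starts. This also stands. The point is therefore limited to what this document instructs.
- **Contact with a protective parent has value.** A rule barring contact with both the implicated adult and that adult's partner would by default cut off a caregiver who could help, and sending every such case to child protection would lower item 3's threshold unannounced. This is right, and the fix below does neither.

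A reader might also infer that item 5 requires the implicated parent to be told. The wording does not support that: on a child's disclosure, informing the participant can mean informing the child, which is ordinary good practice. Nor can one infer that abused children go without referral, because items 3 and 4 provide a route that needs no parental agreement.

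**Conclusion.** The point holds in a limited form. Item 2 is a stated, unconditional instruction. Applied as written after a child's interview that implicates a parent figure, it can expose the child to that adult, and nothing in the protocol suspends the contact or puts services first. Item 5 is ambiguous and lends only weak support.

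The conclusion rests on reading item 2 as reaching child interviews, which its wording permits but does not spell out, and on the referral protocols not already containing an exception, which cannot be checked here. Confidence is medium for both reasons.

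The size cannot be stated. The protocol gives no basis for estimating how many children would come under item 2, and the planned number of children and the item counts should not be read as a measure of risk. A reader might look for bias in the child-reported outcomes. The documents give no basis for that, and none is claimed. The change is worth making because the possible harm to an individual child is serious and the cost is small.

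**What to change.** **Item 2.** Add an exception. When the concern arises from a child's interview and implicates a parent figure or another adult in the household, the researcher does not approach that adult. The researcher takes the concern the same day to the investigator who supervises the research assistants (section 18). That investigator decides whether, when and with which non-implicated caregiver to speak, together with child protection services where item 3's threshold of significant harm is met.

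**Item 5.** State that in such cases the participant to be informed is the child, and not the implicated adult, until that decision has been made.

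Item 3's threshold and the other items stay as they are. If the referral protocols already contain this rule, item 2 should cite it.

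**Cost.** Two items are reworded, with a short addition to the interviewer training already planned under item 6. Contact with a non-implicated parent may be briefly delayed. The change may count as an amendment needing Trials Steering Committee agreement and ethics approval (section 27). Design, sample size and analysis are unaffected.
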